**RESTRUCTURED**

**14.0 STATISTICAL SOFTWARE**

Statistical analyses will be performed [REDACTED]

RESTRUCTURED

## **15.0 STATISTICAL AND DATA HANDLING CONVENTIONS**

### **15.1 SUMMARY STATISTICS**

The following statistical summaries will be presented for each type of data:

- Continuous variables will be summarized by descriptive statistics (number of patients, mean, standard deviation (SD), median, minimum, and maximum values).
- Categorical variables will be summarized by frequency distributions (counts and percentages).
- Time-to-event data will be summarized by showing the number of patients, number of patients experiencing the event of interest, estimates of the median, first quartile and third quartile using the Kaplan Meier estimate as well as a 95% CI for the median

### **15.2 VISIT TIME WINDOWS**

**Table 15.2–1** and **Table 15.2–2** present visits assigned for efficacy and safety analyses and the corresponding range of treatment days (window) during which an actual visit may occur for the OLTP and DBTP respectively.

**Table 15.2–1. Visit Time Windows for Screening and OLTP**

OLTP Visit Timepoint	Visit Number (AVTSIT)	Target Day for Rollover Patients Relative to the First IP Dose during the OLTP (ADY)	Window for Rollover Patients
Screening	Visit 1	1	1
Week 0	Visit 2	8	[2, 11]
Week 1	Visit 3	15	[12, 18]
Week 2	Visit 4	22	[19, 25]
Week 3	Visit 5	29	[26, 32]
Week 4	Visit 6	36	[33, 39]
Week 5	Visit 7	43	[40, 46]
Week 6	Visit 8	50	[47, 53] *
Week 7	Visit 9	57	[54, 60] *
Week 8	Visit 10	64	[61, 67] *
Week 9	Visit 11	71	[68, 74] *
Week 10	Visit 12	78	[75, 81] *
Week 11	Visit 13	85	[82, 88] *
Week 12	Visit 14	92	[89, 95] *

**Table 15.2–1. Visit Time Windows for Screening and OLTP**

OLTP Visit Timepoint	Visit Number (AVISIT)	Target Day for Rollover Patients Relative to the First IP Dose during the OLTP (ADY)	Window for Rollover Patients
Week 13	Visit 15	99	[96, 102]*
Week 14	Visit 16	106	[93, 109]*
Week 15**	Visit 17	113	> 109*
Week 16	Visit 18		NA
Early Termination	Visit 122	NA	NA

\* If rollover patients meet stabilization criteria at Visits 9–17, Visit 18/Week 16 assessments should be completed at that visit.

\*\* Rollover patients who do not meet stability criteria by Visit 17/Week 15 will undergo the End-of-Treatment/Early Termination assessments (Visit 122/Week 104/ET, as shown on the DBTP Schedule of Evaluations).

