## **8.0 EFFICACY ANALYSES**

All efficacy analyses for the OLTP will be performed using the Open-label ITT Population. All efficacy analyses for the DBTP will be performed using the Double-blind mITT Population. The baseline Day 0 assessment of the lead-in study will be used as the baseline for the OLTP. The Day 0 assessment is the last non-missing assessment before the first dose of Double-blind IP during the placebo lead-in period of their respective lead-in study. The last non-missing assessment before the first dose of Double-blind IP in the DBTP will be used as the baseline for the DBTP. All statistical tests will be 2-sided hypothesis tests performed at the 5% level of significance and all CIs will be 2-sided 95% CIs, unless stated otherwise.

The rater-administered MADRS will be used when deriving endpoints for analyses. The computer-administrated MADRS scores will be provided in a listing.

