**Table 15.2–2. Visit Time Windows for DBTP and SFU**

DBTP Visit Timepoint	Visit Number (AVISIT)	Target Day Relative to the First IP Dose during the DBTP (ADY)	Window
Week 0	Visit 18	0	0
Week 1	Visit 19	7	[1, 10]
Week 2	Visit 20	14	[11, 17]
Week $X^a$	Visit “18+ $X^a$ ”	$7 \times X^a$	[ $7 \times X^a - 3, 7 \times X^a + 3$ ]
Final/Early Termination	Visit 122	NA	NA
Safety Follow-up	Visit 123	$Y^b + 14$	$> Y^b$

a  $X$  is an integer from 3 to 104.

b  $Y$  is the study day of the Final/ET visit.

[figure not shown]
If a patient has 2 or more values for a given endpoint within the same window, the value with collection date closest to the scheduled day will be used for analysis; if there are 2 values whose collection dates are equidistant from the scheduled day, the value corresponding to the later date will be used for analysis.

With the exception of endpoints recorded pre or post IP dose and Visit 122/ET MADRS assessments, in the event there are multiple values of the same endpoint on the same date, the last value will be taken as the value for that date. For endpoints reported pre IP dose, in the event there are multiple values of the same endpoint prior to IP dose, the last value prior to the IP dose is taken as the predose value for that date. Similarly, for endpoints reported post IP dose, in the event there are multiple values of the same endpoint after IP dose, the last value will be taken as the postdose value for that date. For multiple MADRS assessments on the same date for Visit 122/ET, the last MADRS assessment prior to Visit 122/ET on that date will be taken as the value for that date.

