**16.0**

**CHANGES TO ANALYSES SPECIFIED IN PROTOCOL**

There are no changes to the analyses specified in the final protocol Amendment 2 (version dated 06 Nov 2018). While there are analyses for endpoints collected during the OLTP that are with respect to Day 0 of the lead-in studies, it was necessary not to explicitly mention this fact in the RAP-MD-04 protocol Amendment 2 in order to protect restricted information pertaining to RAP-MD-01/02/03.

RESTRICTED

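### Table 15.2–1 gives Visit 16 (Week 14, target Day 106) a window of Days 93 to 109, which overlaps Visits 14 and 15; the table's own pattern gives 103 to 109

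*SAP*

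**What the plan says.** Section 15.2 states that Tables 15.2–1 and 15.2–2 "present visits assigned for efficacy and safety analyses and the corresponding range of treatment days (window) during which an actual visit may occur", so the limits are instructions for assigning data to visits. The relevant rows of Table 15.2–1, titled "Visit Time Windows for Screening and OLTP", are:

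| Visit | Week | Target day | Window |
|---|---|---|---|
| 14 | 12 | 92 | 89 to 95 |
| 15 | 13 | 99 | 96 to 102 |
| 16 | 14 | 106 | 93 to 109 |
| 17 | 15 | 113 | after 109 |

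Visit 18 and Visit 122/Early Termination have no window (NA). A footnote covers patients who stabilise at Visits 9–17: "Visit 18/Week 16 assessments should be completed at that visit".

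The selection rule under Table 15.2–2 opens "If a patient has 2 or more values for a given endpoint within the same window". It takes the value nearest the target day or, if two are equally near, the later one. A further rule covers several values on one date.

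Open-label analyses are planned. Section 8.0 says "All efficacy analyses for the OLTP will be performed using the Open-label ITT Population", and Section 16.0 says "there are analyses for endpoints collected during the OLTP that are with respect to Day 0 of the lead-in studies".

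**The concern.** The Visit 16 row conflicts with its neighbours. Its lower limit lies inside the Visit 14 window, and its range takes in the whole of Visit 15. A single assessment on any of those days satisfies two rows of the table, and the SAP does not say which visit it belongs to.

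At stake is whether open-label by-visit results can be reproduced. Patients with a Day 103–109 value are safe at Visit 16, because that value is always nearer to Day 106 than anything earlier. The exposed patients have no such value: those who left the open-label period at Visit 15 or at a late Visit 14, and those who missed Visit 16. For them, three readings are all compatible with the text:

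- A record may match both windows. A Day 93–102 value then counts as Week 14 as well as Week 12 or 13.
- Each record goes to the visit with the nearest target. The slip then has no effect.
- Each record goes to one visit and the later window takes precedence. Every Day 96–102 value then leaves Visit 15, even for patients who attended both visits.

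Two programmers working from this SAP could therefore report different Week 14 counts and means and, under the third reading, different Week 13 figures.

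**Working it through.** **Inputs.** Target days and windows from Table 15.2–1; selection rules from the text under Table 15.2–2.

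**Step 1: the pattern.** For each row, compute lower limit − target and upper limit − target.

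- Visits 3 to 15 (13 rows): −3 and +3 in every row. For example, Visit 14 gives 89 − 92 = −3 and 95 − 92 = +3; Visit 15 gives 96 − 99 = −3 and 102 − 99 = +3.
- Visit 16 as printed: 93 − 106 = −13 and 109 − 106 = +3. Its width is 109 − 93 + 1 = 17 days, against 7 for Visits 3–15.
- Visit 2 (Days 2 to 11, target 8): −6 and +3. Visit 17 is open above Day 109. These two are also irregular, but they are end windows and meet their neighbours without overlap. Visit 16 is the only interior row off the pattern.

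Table 15.2–2 writes the same ± 3 convention as a formula for double-blind Week 3 onward.

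**Step 2: overlaps as printed.** Each study day from 2 to 129 was checked against all windows.

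| Days | Visits claiming them | Number of days |
|---|---|---|
| 93–95 | 14 and 16 | 3 |
| 96–102 | 15 and 16 | 7 |

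The total is 3 + 7 = 10 days. No other open-label windows overlap, and no day is left uncovered.

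**Step 3: what the nearest-value rule does and does not settle.** Distances from the Visit 16 target:

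- Day 93: 106 − 93 = 13
- Day 99 (an on-target Visit 15): 106 − 99 = 7
- Day 102: 106 − 102 = 4
- Days 103–109: at most 3

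If a Day 103–109 value exists, it wins at Visit 16. If not, the rule can select a Day 93–102 value, 4 to 13 days early. An on-target Visit 14 (Day 92) falls outside the printed window and is not captured. The rule chooses among values within one window; it does not choose between windows for one value.

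**Step 4: assignment by nearest target.** Days 93–95 are 1 to 3 days from 92 and 11 to 13 from 106. Days 96–102 are 0 to 3 days from 99 and 4 to 10 from 106. All ten days would go to Visit 14 or 15. This reading makes the slip harmless, but the SAP does not state it.

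**Step 5: the corrected limit.** 106 − 3 = 103. Visit 15 ends at 102 and Visit 17 starts after 109, so a window of 103 to 109 fits exactly. Repeating Step 2 with this limit gives no overlapping days and no gaps from Day 2 onward.

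**The case against.** The best counter-argument is that this is an evident typing slip. The target day and the adjacent windows show what was meant, and a sensible programmer would write 103. The SAP already uses closeness to the scheduled day as its selection principle, which points to the harmless reading. Harm also needs several conditions together: no Day 103–109 value, a value on Days 93–102, that value not held under a visit without a window (Visit 18 or Visit 122/Early Termination), and a program that lets the wider Visit 16 window take it. No specific Week 14 output is visible in the readable text, and no tested hypothesis is involved.

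Most of this stands, and it limits the weight of the point. The slip is probably typographical, values held only under Visit 18 or Visit 122 are not exposed, and the difference between programs is a possibility, not a demonstrated result. Two things remain. The closeness principle is written for several values in one window, so it does not settle membership of two windows. And the third reading above moves Visit 15 values even for patients who have a Visit 16 value, so not all of those conditions are needed for the outputs to differ. A specification should not depend on the programmer noticing the error.

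**Conclusion.** The Visit 16 window is wrong as printed: −13/+3 days where the pattern is ± 3, with ten study days assigned to two visits and no rule to decide between them. A value wrongly taken as Week 14 would be 4 to 13 days before target, against a tolerance of 3 days at Visits 3–15.

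The consequence is limited to open-label summaries by visit. Relapse in the double-blind period is dated from assessment dates and the Relapse CRF (Section 15.3), and the stable-responder criteria rest on observed MADRS scores (Section 2.0), so neither the time-to-relapse analyses nor eligibility for randomization is affected. The number of patients involved and the net direction of any bias cannot be determined from the SAP.

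The conclusion assumes that the digits in the approved SAP are 93 and 109, which should be confirmed in the PDF, and that the open-label analyses use the windows as Section 15.2 says. The correction should be made, but the point does not threaten the trial's main conclusions.

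**What to change.** In Table 15.2–1, change the Visit 16 (Week 14) window from 93–109 to 103–109. The target day and both adjacent windows determine this value, and it removes the whole overlap, so no extra rule for values in two windows is needed. If visit-assignment programs or dataset specifications already exist, check that they use 103. The cost is one number in one SAP table.

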**Table 15.2–2. Visit Time Windows for DBTP and SFU**

DBTP Visit Timepoint	Visit Number (AVISIT)	Target Day Relative to the First IP Dose during the DBTP (ADY)	Window
Week 0	Visit 18	0	0
Week 1	Visit 19	7	[1, 10]
Week 2	Visit 20	14	[11, 17]
Week $X^a$	Visit “18+ $X^a$ ”	$7 \times X^a$	[ $7 \times X^a - 3, 7 \times X^a + 3$ ]
Final/Early Termination	Visit 122	NA	NA
Safety Follow-up	Visit 123	$Y^b + 14$	$> Y^b$

a  $X$  is an integer from 3 to 104.

b  $Y$  is the study day of the Final/ET visit.

[figure not shown]
If a patient has 2 or more values for a given endpoint within the same window, the value with collection date closest to the scheduled day will be used for analysis; if there are 2 values whose collection dates are equidistant from the scheduled day, the value corresponding to the later date will be used for analysis.

With the exception of endpoints recorded pre or post IP dose and Visit 122/ET MADRS assessments, in the event there are multiple values of the same endpoint on the same date, the last value will be taken as the value for that date. For endpoints reported pre IP dose, in the event there are multiple values of the same endpoint prior to IP dose, the last value prior to the IP dose is taken as the predose value for that date. Similarly, for endpoints reported post IP dose, in the event there are multiple values of the same endpoint after IP dose, the last value will be taken as the postdose value for that date. For multiple MADRS assessments on the same date for Visit 122/ET, the last MADRS assessment prior to Visit 122/ET on that date will be taken as the value for that date.

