### 15.3 DERIVED EFFICACY AND SAFETY VARIABLES

The efficacy variables are derived as follows:

- MADRS total score is the sum of the 10 items from the MADRS. If more than 2 items of the MADRS are missing, then the total score will be set to missing
- *Responder* is defined as a patient with  $\geq 50\%$  reduction from Day 0 MADRS total score
- *Remitter* in the randomized treatment period is defined as a patient with MADRS total score  $\leq 10$

For the MADRS [REDACTED], the total score at a particular visit will be calculated using  $(\text{sum of nonmissing items}) \times (\text{total number of items}) / (\text{number of nonmissing items})$  only if the number of missing items is less than the specified number for each variable. Otherwise, the total score will be set to missing.

The primary efficacy parameter was defined in section 8.1. A relapse will be defined programmatically as meeting any of the following criteria:

- An observed MADRS total score  $\geq 18$  for two consecutive assessments as determined from the MADRS data (not the Relapse CRF). The 2 MADRS assessments must occur on different calendar dates.
- An observed increase in CGI-S score  $\geq 2$  compared with that obtained at randomization as determined from the CGI-S data (not the Relapse CRF).

- Marked as a relapse on the Relapse CRF with the primary reason for relapse indicating “Risk of Suicide”.
- Marked as a relapse on the Relapse CRF with the primary reason for relapse indicating “Need for hospitalization due to worsening of depression”.
- Marked as a relapse on the Relapse CRF with the primary reason for relapse indicating “Need for alternative treatment for depressive symptoms”.

The first relapse date for a patient is defined as the earliest assessment date in which any of the relapse criteria mentioned above were met, obtained either from the date recorded on the Relapse CRF (for the primary reasons of “Risk of Suicide”, “Need for hospitalization due to worsening of depression” or “Need for alternative treatment for depressive symptoms”) or the dates of the corresponding MADRS or CGI-S assessments. For the relapses based on MADRS total score  $\geq 18$  at 2 consecutive visits, the relapse date is defined as the assessment date of the first visit of the 2 consecutive assessments.

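### Could the one-value-per-window rule or the missing-item wording change which MADRS and CGI-S values count towards relapse?

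*SAP*

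**What the plan says.** Section 15.2 says that its two window tables "present visits assigned for efficacy and safety analyses". After Table 15.2–2 comes the selection rule: "If a patient has 2 or more values for a given endpoint within the same window", then "the value with collection date closest to the scheduled day will be used for analysis", with ties going to the later date. In the double-blind period the windows are 7 days wide, except Week 0 (one day) and Week 1 (days 1 to 10). Visit 122/ET has no window.

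Section 15.3 defines relapse for programming. The MADRS criterion is an observed total of 18 or more "for two consecutive assessments as determined from the MADRS data (not the Relapse CRF"), and "The 2 MADRS assessments must occur on different calendar dates". The CGI-S criterion needs a single observed rise of 2 or more since randomization, again taken from the scale data. The relapse date is the earliest assessment date that meets any criterion. One sentence slips into other language: for MADRS relapses "at 2 consecutive visits, the relapse date is defined as the assessment date of the first visit" of the pair.

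On incomplete scales, a bullet in Section 15.3 says "If more than 2 items of the MADRS are missing, then the total score will be set to missing". A later, partly redacted sentence prorates the total "only if the number of missing items is less than the specified number for each variable", and otherwise sets it to missing.

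**The concern.** Relapse is the primary efficacy endpoint, Section 15.2 claims efficacy analyses as its scope, and no sentence places the relapse derivation before windowing. Section 15.4 shows that the authors could write such an exemption: it lets all postbaseline assessments count for potentially clinically significant values. A programmer who windowed first could therefore drop the second of two high MADRS scores, or a single qualifying CGI-S. The Relapse CRF could not restore it, because the MADRS and CGI-S criteria exclude that form as a source. A patient who then left the study would be censored just as depression worsened, so an event would be lost and the censoring would be informative. The switch from assessments to visits adds to the doubt.

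On missing items, the only number shown for the MADRS is 2. If that is also the specified number, the bullet keeps a total with exactly 2 missing items and the proration sentence discards it.

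**Working it through.** **What windowing first would do.** The Week 4 window is days 25 to 31 and Week 5 is days 32 to 38. Four hypothetical patients, derived both ways:

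| MADRS by day | All assessments | Windowed first |
|---|---|---|
| 28: 20; 31: 21; 35: 12 | relapse, day 28 | no relapse |
| 28: 20; 32: 21; 35: 12 | relapse, day 28 | no relapse |
| 28: 20; 31: 12; 35: 19 | no relapse | relapse, day 28 |
| 25: 20; 28: 21; 35: 20 | relapse, day 25 | relapse, day 28 |

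The two routes can differ, and they can differ in either direction.

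**When this can arise.** If the first reading falls evenly over a 7-day window, a second reading g days later shares the window with probability (7 − g)/7: 6/7 = 86% for 1 day, 5/7 = 71% for 2, 4/7 = 57% for 3, and 0 for 7. Readings on a weekly rhythm therefore do not collide, except possibly in Week 1. The issue needs an extra reading between weekly ones, and the SAP does not say how often that happens.

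**What Section 15.3 requires.** It names the scale data as its source, asks for observed scores, counts assessments and dates the event by assessment. Its spacing condition is only that the dates differ, so pairs 1 to 6 days apart qualify. Under windowing that condition would have little to do, though not nothing: a Visit 122/ET reading has no window and could share a date with another. It supports the all-assessments reading without proving it. In the sentence that says visits, the same pair is then called assessments, so the two words are used as synonyms.

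**Size, as a scenario only.** Section 13.0 gives 200 per group, 19% placebo relapse and 20% dropout per 26 weeks, and a hazard ratio of 0.475. With exponential times and 52 weeks of follow-up for everyone (an assumption):

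- Placebo relapse hazard: −ln(0.81)/26 = 0.00810 per week. Rapastinel: 0.475 × 0.00810 = 0.00385. Dropout: −ln(0.80)/26 = 0.00858.
- Expected relapses = 200 × h/(h + d) × (1 − exp(−52(h + d))), with h the relapse and d the dropout hazard: 56.3 on placebo and 29.5 on one rapastinel arm, 85.8 in all.
- Power is 91.0% by Freedman's formula, close to the stated 90%, and 93.2% by Schoenfeld's, Φ(√D × |ln 0.475|/2 − 1.96), with D the number of events.
- If 10% of events were lost, D = 77.2 and Schoenfeld power is 90.5%; if 20%, D = 68.6 and power is 87.0%.

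Starting instead from the 75.84 events that give exactly 90%, the same losses give 86.8% and 82.6%. The loss fractions are assumed inputs in both cases; nothing in the SAP supports any of them.

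**Missing items.** With 8 items answered and summing to 15, the prorated total is 15 × 10/8 = 18.75, which meets the threshold of 18. If the specified number is 2, that total is missing. If it is 3, fewer than 3 missing items is the same as not more than 2, and the two sentences agree.

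**The case for a change.** The strongest case for acting is that two programmers reading the SAP literally could produce different event counts for the primary endpoint, and that one added sentence would prevent it. It is true that no explicit order of operations is given, that Section 15.2 names efficacy analyses without reserve, and that the missing-item threshold in the proration sentence is not visible. That much stands.

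The harm argued from it does not. Section 2.0 ends the double-blind period with the last scheduled assessment at Visit 122 or ET, so a patient who is withdrawn is due another visit, and that visit has no window. How an ET value interacts with a weekly window is not spelled out, but this falls short of showing a lost event. Nor would windowing only lose events, as the third patient above shows. The suggestion that an unscheduled CGI-S usually lies further from the target day than the scheduled one has no source in the document. The missing-item clash rests on supplying a number for a partly redacted sentence that covers the scales collectively.

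**Conclusion.** No change is needed. The window point is an unstated order of operations, not a contradiction: the specific derivation in Section 15.3 governs the primary endpoint, and a statistician following it takes all observed rater-administered assessments in date order. On that reading no relapse is lost, created or moved. The use of visits for assessments in one sentence is a clerical slip.

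If windowing were applied first in error, the effect would depend on extra readings between weekly ones. Its frequency and net direction cannot be derived from the document, so neither bias nor a loss of power has been shown.

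The missing-item point concerns only totals with exactly 2 items missing, and only if the unstated number is 2. The bullet gives a clear MADRS rule, and an analyst would apply it. The conclusion rests on the specific relapse rule taking precedence over the general windowing convention, and on the redacted sentence being consistent with the bullet.
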